The evaluation consists of two stepped-wedge cluster randomised trials running concurrently in Nigeria and Tanzania. The REaCH intervention will be rolled out to all clusters over the course of the trial in a staggered fashion and the order that clusters receive the intervention will be randomised. The evaluation will comprise both the quantitative trial outcomes and a process evaluation. The

evaluation in each country will be conducted independently; comparisons between results will be predominantly qualitative. As a secondary analysis we will estimate the between country difference in treatment effects, although the trials are not designed for this purpose.

Methods: Participants, interventions, and outcomes

Study setting

We propose two identical trials in contrasting countries with marginalised populations: 1) Rural/remote, low income Tanzania in East Africa and 2) Urban and peri-urban in middle income Nigeria in West Africa.

Participants

Health workers and patients receiving healthcare from participating primary care facilities. Tier 1 trainees are doctors/nurses/ medical officers who speak, read and write in English, tier 2 are other cadres e.g. community health workers, pharmacy assistants, receptionists etc who may communicate in English or in local languages. The tier 1 and tier 2 trainees work as a team within the facility.

Eligibility criteria

Primary care facilities

Recruited primary care facilities will individually, or in collaboration with other smaller facilities, become a research cluster. We will recruit 20 clusters which must have 1) a minimum of 100 active patients with one of the eligible long-term conditions attending for healthcare three times per year. Active patients are those for whom there is record of a consultation within the previous five months. 2) paper-based or electronic record keeping of patient names, phone number, age, sex, appointments attended and with whom and pharmacy/investigation records 3) employ a minimum of five health workers. At least one must be tier 1 with the remainder a mix of tier 1 and 2 providing healthcare to citizens 4) Facility managers consent to all parts of the study including process evaluation.

Health workers

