For each module there is a narrated presentation and between 1-3 short assignments for each trainee to undertake and upload onto the Moodle platform. Within each module there is a reflective exercise on planning the cascading of that particular topic to others. Trainees work in virtual cohorts of approximately 12. Each cohort has four peer group/facilitator WhatsApp chats during the three weeks of study. Trainees upload completed module assignments onto the Moodle which their facilitator reviews. These reviewed assignments are the basis for the certificate of attendance awarded at course completion.

Comparison intervention: Usual care delivered in the routine way for each facility. Our stakeholder consultation indicates that this will be face to face care for most patients with occasional informally provided remote telephone consultations for friends and family members of the health worker.

Training procedure

Once the participants give their consent, they are given orientation about the course and offered the trainee's course guide with an overview about the course and the duration, mode of delivery and the learning process, the learning support they can expect, and how the course will be evaluated. In addition, they are given a Moodle guide to enable them to register and access the materials in the Moodle platform. During the learning process the participants can interact and exchange their views through the Moodle forum. The facilitator also has a guide i.e. facilitator guide, to assist him/her in delivering the course. Trainees are informed that they will be required to undertake a short interview at the end of their training with their facilitator to assess their learning. This structure serves the purpose of motivating trainees to engage with the training, self-directed learning activities and the peer-discussion and it provides a quality assurance process to assess and confirm their learning prior to being permitted to deliver cascade training. Trainees have to satisfactorily complete to receive their certificate. The award of the certificate is required to continue cascade learning to colleagues and to continue participation in the trial.

Outcomes

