We propose four primary outcomes, detailed below, to test our research hypothesis. Multiple primary outcomes are recommended against by some guidance for cluster trials (e.g. CONSORT) [10] as it "incurs the problems of interpretation associated with multiplicity of analyses". However, we opt for multiple primary outcomes here as the intervention is multi-faceted and may affect different aspects of patient care and their interaction with the health system in different ways. Appropriate inferences about the functioning of REaCH cannot be made on the basis of any singular outcome. We ensure appropriate correction for multiple testing for all our test statistics (see Statistical methods). Furthermore, we will not be using 'statistical significance' to make inferences about the effectiveness or not of the intervention, given the importance of including the full range of qualitative and quantitative evidence to make conclusions about the effectiveness of REaCH, which also limits the risk of faulty inferences made through the use of multiple primary outcomes. Our unit of analysis for all outcomes is at the individual level.

Primary outcomes:

- 1) Trust in healthcare provider: Physician Humanistic Behaviour Questionnaire (PHBQ) [11] determines the degree to which healthcare providers communicate humanistically with their patients. Humanistic communications engender trust between the patient and the healthcare worker. The PHBQ has face and content validity with patients and health workers for assessing these behaviours during remote consultations [12].
- 2) Face to face consultation rate: the number of visits per month for the eligible patient population where the patient is seen in person by the consulting health worker.
- 3) Remote consultation rate: the number of visits per month for the eligible patient population conducted using a telephone.
- 4) Prescribing rate: the number of prescriptions issued and collected to the eligible patient population per month. This outcome is a proxy for patient safety as a change in this outcome is an indicator of changes in safety and confidence. The meaning and impacts of changes in this indicator will be explored in the process evaluation.

Secondary outcomes:

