This method of recruitment and sampling limits the amount of information to be collected each month, enables the tracking of patients each month to maintain the open cohort within each clinic, it simplifies the sampling process, and maintains patient confidentiality.

[figure not shown]
The research participation response rate experienced by our partners range from 60-80% and we will sample 30 patients each month to achieve our target sample of 20 per month.

Methods: Assignment of interventions

A number of outcomes will be collected by interviewing a random sample of 20 patients who have received a consultation in the previous month. To reduce the transfer of patient identifiable data and their contact details, we specify the following sampling protocol. On the first calendar day of each month the list of patients who have had at least one consultation in the preceding month will be aggregated within each cluster site by the facility representative. The list will be pseudonymised by redacting identifiable information including patient name and contact details but keeping unique IDs, such as row numbers, and other basic data to permit comparisons between sampled and interviewed

groups for quality control. The list will be photographed and sent to the trial statistician, who will send back a random sample. Data collection from the selected patients can then proceed.

Figure 1: Cluster randomisation sequencing

Allocation

Within each country the 20 participating clusters will be randomised to one of ten sequences (see figure 1) with two per sequence. A random number will be generated for each cluster and then clusters assigned to each sequence in ascending order of the generated number. The randomisation will be conducted by the trial statistician who will be blinded to cluster name. The intervention implementers and clinics will not be blinded to allocation sequence as this is impractical given the need to plan and prepare training.

Blinding

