Appendix 1 shows the data flow for patient participants through the trial.

Statistical methods

The data from each trial will be analysed using a generalised linear mixed model framework standard for stepped-wedge cluster designs[16]. Data from each time point are considered a repeated cross-section given the difficulty linking observations between patients in different time periods. The primary outcomes are of two types: count data (the number of consultations by mode of delivery and the number of prescriptions) and a continuous score (the patient trust outcome). For the former we

specify the following log-linear model, for patient $i = 1, \dots, N$ in cluster $j = 1, \dots, J$ at time period $t = 1, \dots, T$ with number of events y_{ijt}^1 :

$$y_{ijt}^{(1)} \sim \text{Poisson}(\lambda_{ijt})$$

$$\lambda_{ijt} = N_{jt} \exp(\eta_{ijt}^{(1)})$$

where N_{jt} is the denominator population (i.e. the number of active patients in cluster j at time t) and η_{ijt} is the linear predictor. For the continuous outcome y_{ijt}^2 we specify:

$$y_{ijt}^{(2)} \sim N(\eta_{ijt}^{(2)}, \sigma^2)$$

The specification of the linear predictor in both models takes the form:

$$\eta_{ijt} = x'_{ijt}\beta + z'_{jt}\gamma + \delta D_{jt} + \alpha_j + \psi_{jt}$$

where x_{ijt} is a vector patient-level covariates, z_{jt} is a vector of cluster-level covariates, D_{jt} is an indicator equal to one if cluster j has the intervention at time t and zero otherwise, and $\alpha_j \sim N(0, \sigma_\alpha^2)$ and $\psi_{jt} \sim N(0, \sigma_\psi^2)$ are cluster, cluster-time and individual random effects respectively. The treatment effect of interest from the Poisson model is an incidence rate ratio, although we will also provide absolute treatment effects for context, and from the linear model we will report only absolute treatment effects.

Inference

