In all trial clusters we will survey facility managers and tier 1 trainees on implementation one month after completion of the REaCH training for the cluster. The timing allows them time to have reflected on the training and start planning delivery. The questionnaire provides the participant opportunity to reflect on implementation. We will collect information on how facilities distributed the airtime allowance across tier 1 and tier 2 trainees.

Observation, interview and prescription data will be collected in each country, from a random sample of five facilities (clusters) who receive the intervention during the first 6 months of the trial, to allow time for implementation prior to data collection.

Consent to process evaluation data collection will be taken along with consent to trial participation.

Training data (all clusters)

Prior to each REaCH training the facilitator will confirm consent to the use of aggregate data about the trainees/training and to the use of trainees' text for analysis in the study process evaluation clarifying that all personal identifiers will be removed before it is shared with the research team. This will be repeated at the end of the training. Trainees will be able to confidentially inform the facilitator if they do not wish their text to be included.

Survey of facility manager and trainees (all clusters)

All tier 1 trainees and the facility manager in all clusters will be invited to complete a questionnaire about implementation of remote consulting.

Observation (2x5 clusters)

We will observe two tier 1 and two tier 2 training sessions. Each REaCH facilitator will provide us with their timetable for training delivery. We will take a stratified random sample of planned training sessions to ensure observation of the range of modules within the training. Where individuals scheduled to attend observed training sessions have not given consent to be observed we will discuss with them their options. They may choose to attend but remain silent or they may choose not to attend. They will be offered a briefing session with the facilitator after the session so they are able to catch up on learning.

Semi-structured telephone interviews (2x5 clusters)

We will interview 3-4 months after training

- the facility manager
- the REaCH facilitator
- two tier 1 and two tier 2 health workers
- four patient trial participants

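### Read literally, the certificate rule removes uncertified tier 1 trainees from an implementation survey and interviews meant to cover tier 1 trainees whether or not certified

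*Protocol*

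**What the plan says.** The Training procedure section describes an end-of-training interview with the facilitator, which confirms learning before a trainee may cascade. It then sets the pass condition, "Trainees have to satisfactorily complete to receive their certificate", and its consequence: "The award of the certificate is required to continue cascade learning to colleagues and to continue participation in the trial". The section just before it describes the same document more loosely: "These reviewed assignments are the basis for the certificate of attendance awarded at course completion".

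The Participants section counts health workers as trial participants alongside patients. The timeline section keeps them in the trial for one to six months, depending on training date and involvement in the process evaluation. The facility staff consent section covers training, cascading, Moodle data, interviews and implementation survey questions.

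Under Process evaluation, Participants and sampling, the protocol says that in all clusters "we will survey facility managers and tier 1 trainees on implementation one month after completion" of the training. The survey subsections there extend the invitation to every tier 1 trainee and the facility manager. In five clusters per country, two tier 1 workers are to be interviewed three to four months after training.

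On staffing, the facility eligibility criteria say of the health workers: "At least one must be tier 1 with the remainder a mix of tier 1 and 2". On randomisation, the Allocation section says: "Within each country the 20 participating clusters will be randomised to one of ten sequences".

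**The concern.** The sentence attaches two consequences to the certificate. The first, permission to cascade, is part of how the intervention is delivered, and the protocol justifies it. The second, staying in the trial, has no stated reason and depends on a result of the training being evaluated.

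Trainees who do not complete satisfactorily are likely to include those who engaged least or found the course hardest to fit into their work. Their answers on acceptability, appropriateness and feasibility are among the most informative the process evaluation could collect. If they leave before the survey and interviews, those results describe satisfactory completers only. The protocol relies on this material: the Outcomes section bases conclusions about effectiveness on qualitative and quantitative evidence together, and the survey analysis is meant to help interpret the trial results.

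**Working it through.** The protocol gives no figure for certification failure, so there is none to reproduce. The check traces whom the rule removes, and then sizes the loss under stated assumptions.

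**1. Order of events for a tier 1 trainee**
- Training runs over two to three weeks and ends with the assessment and certificate decision.
- The implementation survey comes one month after completion.
- Interviews, in sampled clusters, come three to four months after training.

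The certificate sentence names cascading separately. Of the activities in the staff consent section, what remains after training is mainly the survey and the interviews, so these are what the clause on trial participation would end. For an uncertified trainee, that clause and the invitation to all tier 1 trainees cannot both be followed.

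**2. Number of trainees affected**
- Planned tier 1 trainees: 80 over both countries (Training and capacity building section).
- Clusters: 2 × 20 = 40, so 80 / 40 = 2 trainees per cluster on average; the eligibility minimum is 1.
- Assumed failure rate f: 5% to 20% (not from the protocol).
- Trainees lost = 80f: 80 × 0.05 = 4, and 80 × 0.20 = 16.

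**3. Effect on a survey mean**

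With completers' mean m_c and uncertified trainees' mean m_u, the mean over all trainees is (1 − f)m_c + f·m_u. Surveying completers only overstates it by f(m_c − m_u). On the 5-point scale, for assumed gaps:

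| Gap (points) | f = 5% | f = 20% |
|---|---|---|
| 0.5 | 0.025 | 0.10 |
| 1.0 | 0.05 | 0.20 |
| 1.5 | 0.075 | 0.30 |

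**4. Effect on the protocol's own targets**
- The survey aims for at least two questionnaires per cluster. In a one-trainee cluster the possible respondents are the manager and that trainee, so one failure leaves one and the target cannot be met.
- In a sampled two-trainee cluster, one failure leaves one of the two planned tier 1 interviews.

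**5. Does the rule touch the primary outcomes?**
- The remote consultation rate is "the number of visits per month for the eligible patient population conducted using a telephone". Face-to-face and prescribing rates use the same eligible population.
- The denominator in the count model is "the number of active patients in cluster j at time t" (Statistical methods).
- Patients for the trust questionnaire are sampled at random from everyone who consulted in either mode.

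None of these depends on the certificate. The timeline section has facilities supplying data in months 2 to 13 without a certificate condition. Patients of uncertified workers therefore stay in the analysis, and any failure of training dilutes the estimate as it should. Exclusion bias as written is zero.

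**6. What it would take to bias the effect**

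A cluster with no certified tier 1 trainee would have to be dropped, or have its indicator D_jt set to zero. The expected number of such clusters out of 20 per country, assuming independent failures, is:
- one trainee each, 20f: 20 × 0.05 = 1 to 20 × 0.20 = 4;
- two trainees each, 20f²: 20 × 0.0025 = 0.05 to 20 × 0.04 = 0.8.

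As an illustration, take a remote-consultation rate ratio of 1.56 in trained clusters (the upper detectable value in the Sample size table, used only as an example) and no effect in a share q of clusters. Keeping all clusters gives about 1 + (1 − q)(1.56 − 1):
- q = 0.04 (two trainees each, f = 20%): 1.54;
- q = 0.20 (one trainee each, f = 20%): 1.45.

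Dropping those clusters would report 1.56 instead.

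**The case against.** The strongest defence is that the sentence is loose wording about trainees. It may mean only that an uncertified trainee does not go on to deliver the cascade, and the survey text is explicit that all tier 1 trainees are invited. The survey analysis also compares respondents by whether they received the training, which does not look like a completers-only design. Managers respond whatever their staff achieved, and engagement with the training is recorded for all clusters. The certificate is in one place described as one of attendance, so failures may be rare.

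Much of this stands. The survey is not written as completers-only, so the tilt is a risk arising from two conflicting instructions and not an established feature of the results. The failure rate is an assumption. However, the conflict itself is in the text, and a local team following the Training procedure section would be entitled to stop contact with an uncertified trainee. Aggregate engagement data do not replace that trainee's views.

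A reader might go further and infer a post-randomisation exclusion that inflates the effect of REaCH. The protocol does not support that. Clusters are randomised, not trainees, and no text removes or recodes a cluster because a trainee failed. The analysis of clusters with incomplete training may also be covered in a statistical analysis plan that is not at hand. Nor is there a single favourable direction: no change is hypothesised for trust, and a change in prescribing either way needs interpretation.

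**Conclusion.** The point holds as a contradiction within the protocol that affects the process evaluation. The Training procedure section ends trial participation for uncertified trainees; the Process evaluation section requires all tier 1 trainees to be invited afterwards. If the first is followed, acceptability and feasibility results lean towards satisfactory completers. For failure rates of 5% to 20% and score gaps of 0.5 to 1.5 points, all assumed, the overstatement is 0.025 to 0.30 on a 5-point scale, with 4 to 16 of 80 trainees lost.

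The primary effect estimates are not biased as written. The remaining exposure is conditional: D_jt is defined by whether the cluster has received the intervention and is not expressly tied to the allocated month, so a cluster with nobody certified to cascade might be judged untreated. The permutation test, which re-randomises clusters to sequences, fits coding by sequence, but the protocol should say so. The change is worth making because the conflict is plain and the remedy nearly free.

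**What to change.** - In Training procedure, limit the sentence to cascading: the certificate is needed to cascade training, and trial participation does not depend on it.
- In Process evaluation, state that uncertified tier 1 trainees stay in the survey invitation and the interview sampling frame, subject to their consent.
- Report the number of tier 1 trainees certified per cluster as an implementation result.
- As a safeguard, add to Statistical methods that every randomised cluster stays in the trial and is analysed from its allocated training month, whatever its trainees' certification.
- Reconcile the description of a certificate of attendance with the requirement for satisfactory completion.

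The cost is a few sentences. Clinics already supply monthly data and trainee engagement is already collated, so no new cluster data are needed. The extra work is contacting the few uncertified trainees, whose inclusion may make the acceptability and feasibility scores less favourable.

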- 5) Patient engagement with their health: Patient Activation Measure (PAM-13) aims to understand the knowledge, beliefs and skills required by people to enable them to manage their long-term conditions [13]. It has been successfully used in African populations [14]. Our previous research found that patient activation increases with remote consulting [4]. Also that the PAM-13 [12] has face and content validity for assessing the impact of remote consulting.
- 6) Patient safety is assessed by counting the number of investigations processed by the facility monthly and matching these to the patient’s consultation type. An increase may indicate a higher safety threshold when the person cannot be examined. A decrease may indicate missed health needs. The meaning and impacts of changes in this indicator will be explored in the process evaluation.

Evidence from the secondary outcomes will be explored in the process evaluation.

Sample size

The trials in Nigeria and Tanzania will take place independently, but with identical designs. We plan to recruit 20 clusters in each country for the trial and we expect there to be an average of 100 active eligible patients at any one time in each cluster. We describe each of these active patients in each cluster as an open cohort- patients will leave the cohort if they are not seen for >5 months and newly diagnosed patients meeting the eligibility criteria can join the cohort. The trial has both non-inferiority and superiority inferential goals: we hypothesise the intervention will increase the remote consultation but not affect consultation trust, for example. We therefore opt to determine “minimum detectable effect” sizes rather than power to indicate the precision of the trial and the likely sizes of effect for which we can provide strong evidence of superiority or non-inferiority. Our calculations are based on the statistical models reported below and a power of 80%, a type I error rate of 5%, an ICC of 0.05, and a CAC of 0.8. The assumptions about each outcome and minimum detectable effect sizes are reported in the Table below.

| Outcome | Baseline assumed | Denominator or population | Treatment effect | Lower minimum | Upper minimum |
|----------------|-------------------------|----------------------------------|-------------------------|----------------------|----------------------|

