|----------------|-------------------------|----------------------------------|-------------------------|----------------------|----------------------|

| | | | | detectable effect | detectable effect |
|--|--|-----------------------------|----------------------|--------------------------|--------------------------|
| Face to face consultation/prescription rate | 0.25 consults/prescriptions per person-month | All active patients (n=100) | Incidence rate ratio | 0.84 | 1.20 |
| Remote consultation rate | 0.02 consults per person-month | All active patients (n=100) | Incidence rate ratio | 0.77 | 1.56 |
| Patient trust | 3.5 (sd=0.5) | Sampled patients (n=20) | Absolute effect | -0.07 | 0.07 |

A change in either consultation rate of an equivalent of one visit per person-year is considered “clinically significant”, which is well outside our minimum detectable range. Similarly, we will be able to identify reasonably small changes (~0.15 standard deviations) in patient trustworthiness score, although we do not hypothesise a change in this outcome.

Patient participant recruitment and sampling

At the study commencement each cluster provides the study with a pseudonymised list of active patients, giving us a patient ID and the basic information, we need from each patient (age, sex and eligible diagnosis). At the clinic they will have a link to patient ID with the patient’s record but we will not have access to the patient personal data. This is the open cohort for each cluster.

Each month we collect from each clinic a record of the consultations conducted and prescriptions and investigations ordered by the clinic, all they need to provide is the number of visits by type, prescriptions, investigations and any other information we need linked to a patient ID (e.g. patient 1234 had one remote visit, 2 prescriptions). Any additional patients can join the open cohort if they become eligible during the trial period.

Using the information, the research team can calculate outcomes, remove patients that are no longer active/who default, and sample for participation in the trust and patient activation outcomes and the process evaluation interviews. We will return the list of sampled patient identification number to the clinic for them to contact the potential participant so the research team can commence the informed consent processes.

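### The denominator of the three rate outcomes depends on consulting, so lasting loss of care is hidden after about five months of exposure

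*Protocol*

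**What the plan says.** Four places in the protocol combine to produce the rule.

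- Eligibility criteria, Primary care facilities: "Active patients are those for whom there is record of a consultation within the previous five months".
- Sample size: in the open cohort, "patients will leave the cohort if they are not seen for >5 months".
- Patient participant recruitment and sampling: from the monthly clinic returns the research team will calculate outcomes and "remove patients that are no longer active/who default".
- Statistical methods: the Poisson offset "is the denominator population (i.e. the number of active patients in cluster j at time t".

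The Outcomes section words the rates differently. The face-to-face rate, for example, is "the number of visits per month for the eligible patient population where the patient is seen in person", and the patient eligibility criteria contain no activity rule. Of the prescribing rate it says "This outcome is a proxy for patient safety". The research hypothesis is that remote consulting rises while trust and safety are unaffected.

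**The concern.** Activity is judged from the same monthly records that supply the outcomes, so membership of the denominator after crossover depends on the outcome and may depend on the intervention. A patient who falls out of care, and is no longer prescribed for, is the case the safety proxy should register. Under the rule that patient contributes zeros for about five months and then leaves the numerator and denominator together, after which the rate among those who remain looks normal.

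No other listed outcome clearly fills the gap.

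- The Harms section compares prescription and investigation rates by consultation type, so a patient with no consultation cannot contribute.
- The trust and activation surveys sample only patients who consulted in the month.
- The investigations outcome is worded as "counting the number of investigations processed by the facility monthly", matched to consultation type. It does not use this denominator, but the matching again needs a consultation.
- Missed appointments are a research question and a collected dataset (Table 1), but not a listed primary or secondary outcome.

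**Working it through.** **Inputs from the protocol.** Baseline 0.25 consultations or prescriptions per person-month; 100 active patients per cluster; ICC 0.05; CAC 0.8; power 80%; two-sided 5%; 20 clusters in 10 sequences; 12 monthly data periods (months 2–13); five-month activity window; clinically significant change of one visit per person-year, which is (1/12)/0.25 = one third of baseline (ratio 0.67 or 1.33). **Assumed:** the share of patients who leave care, the timing of their visits, and how much patients differ.

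**1. The plan's own precision figure.** This is the generalised least-squares variance for a cross-sectional stepped wedge with cluster and cluster-period random effects and fixed period effects. Residual variance per person on the log scale is 1/0.25 = 4. Between-cluster variance is 4 × 0.05/0.95 = 0.21, split 0.8 to 0.2 between cluster and cluster-period. The detectable ratio is exp(±(1.96 + 0.84) × SE). With 12 periods this gives 0.835 and 1.198, against the stated 0.84 and 1.20, so it reproduces.

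**2. How often the rule bites.** With randomly timed visits, P(no visit in 5 months) = exp(−5 × 0.25) = 29%. After a fall of one visit per person-year it is exp(−5 × 0.167) = 43%. On a regular four-monthly schedule, one missed visit is enough for removal.

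**3. Complete loss of care: 20% stop attending at crossover (assumed).** The true ratio is 0.80 in every exposed month. Under the rule, the ratio in exposure month k is 0.8A / (0.8A + 0.2P_k), where A = 1 − exp(−1.25) = 0.713 and P_k = 1 − exp(−0.25 × (6 − k)) for k up to 5, and 0 afterwards.

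| Exposure month | 1 | 2 | 3 | 4 | 5 | 6 onward |
|---|---|---|---|---|---|---|
| P_k | 0.713 | 0.632 | 0.528 | 0.393 | 0.221 | 0 |
| Ratio under the rule | 0.80 | 0.82 | 0.84 | 0.88 | 0.93 | 1.00 |
| Ratio, denominator fixed | 0.80 | 0.80 | 0.80 | 0.80 | 0.80 | 0.80 |

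A regular four-monthly schedule gives nearly the same path. If the first sequence crosses after one of 12 periods, there are 2 × (11 + 10 + … + 2) = 130 exposed cluster-months. Of these, 2 × (6 + 5 + 4 + 3 + 2 + 1) = 42, or 32%, are at exposure month 6 or later.

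**4. What one constant effect would report.** The step 3 path was put through the step 1 model, fitting a single effect.

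- With fixed period effects: about 0.78–0.80.
- Without period effects: about 0.87–0.88.
- Simple average over exposed months, for comparison: 0.89–0.90.

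The first result lies close to the truth only because a constant-effect stepped-wedge fit leans on the early exposure months, before anyone has been dropped. The linear predictor in Statistical methods prints no explicit period term; period could enter through the covariate vectors.

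**5. Uniform change in visit frequency (true 0.67).** If patients differ (assumed coefficient of variation 0.7) and returners do not count until they are active again, the monthly ratio drifts from 0.67 to about 0.70, and the fit with period effects gives 0.67. If a returner re-enters in the month of the visit, the late ratio with identical patients is [0.167/(1 − exp(−1.0))] / [0.25/(1 − exp(−1.5))] = 0.264/0.322 = 0.82. The single effect fitted without period effects is then about 0.74. The fitted range is therefore about 0.67–0.74.

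**6. Two modes of contact.** Simulation with remote contact assumed to count as being seen, and remote rising from 0.02 to an assumed 0.10 per month:

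- Remote replaces face-to-face (0.25 to 0.17): true face-to-face ratio 0.68, observed 0.68.
- Remote is added and face-to-face is unchanged: true 1.00, observed 0.93–1.00.
- Remote rate in both scenarios: true 5.0, observed 4.6–5.0.

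**The case against.** An open cohort of current service users is a legitimate population, and the activity rule guards against stale patient lists in paper-based facilities. The 20% loss is not a protocol figure. For the protocol's own clinically significant change, the fitted ratio stays at or below 0.74, beyond the detectable 0.84. The analysis fits one effect over all exposed months, and late sequences have fewer than six of them. Missed appointments are collected, the process evaluation will explore changes in prescribing, and sensitivity analyses often belong in an SAP, which is not at hand.

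Most of this stands as a limit on size. A reader might infer that all three rates are biased towards no effect, or that lost care vanishes from the results. The documents support neither. Substitution leaves the face-to-face ratio unbiased, and added remote contact can push it away from the null. The remote rate, which is expected to rise, is barely affected. Patients who leave care are counted as zeros for about five months, and with period effects the single estimate can land near the truth.

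What the objection does not answer is the structure. The protocol itself fixes the denominator, so this is not a detail left to the SAP. No passage keeps removed patients in a denominator or counts exits as an outcome.

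**Conclusion.** The point holds in a limited form and should be fixed. The denominator of the three rate outcomes is determined after crossover by consulting, which is itself an outcome. The main consequence is that lasting, complete loss of care is hidden from about exposure month 6 and in the absolute rates that the protocol says it will report for context. A near-correct single estimate would describe only the first months of exposure.

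In the 20% example the true ratio of 0.80 reads 0.80 rising to 1.00. The fitted effect is 0.78–0.80 or 0.87–0.88 according to whether period effects are included, so it falls on either side of the detectable 0.84. Distortion of a uniform change is smaller. The direction for the face-to-face rate depends on whether remote contact counts as being seen, which the protocol does not state.

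Confidence in the mechanism is high and in the size moderate. The size rests on the assumed loss, on visit timing and on the 10-sequence, 12-period layout. The six-sequence Tanzania redesign in Appendix 5 was not modelled.

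**What to change.** - Analyse the three rates with every enrolled patient ID kept in the denominator from entry (the baseline list, or the month of joining), with zero counts in months without contact. Write explicit period effects into the model. Report this beside the active-only analysis.
- Report exits from the active cohort by period and by intervention condition, as a loss-from-care outcome.
- Show effects by exposure time as well as the single constant effect. Where loss builds up gradually, one constant effect is a poor summary with either denominator.
- State whether a returning patient re-enters the cohort and from which month, and whether a remote contact counts as being seen.
- Align the outcome definitions, which name the eligible population, with the denominator used.

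**Cost.** The ID-linked monthly lists are already collected, so the main analysis needs protocol wording and some programming. The downside is that patients who have moved or died unrecorded stay in as zeros. These build up over calendar time and so fall mostly in trained months. The analysis then relies on the period adjustment, or on asking clinics to flag known deaths and transfers. Table 1 does not list either item, so that option adds a small data request.
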